It is planned to randomize 372 participants with 186 in each of 2 cohorts who have received primary vaccination with either COVISHIELD OR COVAXIN. Assuming that the proportion of non-evaluable participants \leq 15% (which leads to a sample size of 158 evaluable participants for each cohort), group sample sizes of 93 each in the tested vaccine group and the active control group achieve at least 80% power to detect non-inferiority using a one-sided, two-sample t-test. The margin of non-inferiority is -0.33. The true ratio of the means at which the power is evaluated is 1.00. The onesided significance level (alpha) of the test is 0.025. The coefficients of variation of both groups are assumed to be 1.1. Non-inferiority of COVOVAX booster over an active control vaccine group for each cohort will be concluded separately if the lower limit of the two-sided 95% CI for the GMT ratio for both anti-S IgG and neutralizing antibodies between COVOVAX and the active control vaccine at Day 29 is > 0.67. The same sample size to serve the statistical test for a non-inferiority difference in proportion of participants achieving ≥ 2-fold increase in Anti-S and nAbs between COVOVAX and the active control vaccine at Day 29 will achieve 82% power, using a one-sided, two-sample z-test at alpha level of 0.025. Proportion of participants achieving \geq 2-fold increase in both Anti-S and nAbs for COVISHILED/ COVAXIN arm is assumed 95% and the margin of non-inferiority is -10%. The true difference of the proportion at which the power is evaluated is 0. Sample size calculations were performed using a non-inferiority test for the ratio of two means and difference in two proportions in PASS 15.0.7 Version software.

To assess the co-primary objectives, the non-inferiority hypotheses will be tested on the GMR between COVOVAX and COVISHIELD or COVOVAX

Confidential Page 15 of 94

and COVAXIN for anti-S IgG and nAbs at 28 days (Day 29) post study vaccination using an ANCOVA model for each cohort. The lower limit of the 95% CI will be compared with the non-inferiority margin 0.67 and COVOVAX will be declared non-inferior to the active Control vaccine, COVISHIELD or COVAXIN in each cohort if it is greater than 0.67.

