The non-inferiority hypothesis of difference in proportions of participants with at least 2-fold increase in anti-S IgG and nAbs at Day 29 between COVOVAX and COVISHIELD or COVAXIN will be examined using the Miettinen and Nurminen method for 95% CI of the difference. If the lower limit is greater than the margin, -10%, then the non-inferiority of difference in proportions of participants with at least 2-fold increase in anti-S IgG and nAbs will be declared.

Detailed statistical analytical methods will be provided in statistical analysis plan (SAP) which will be prepared and approved before database lock.

An interim analysis is planned after completion of 28 days follow up after the vaccination of all study participants from each cohort separately or together depending on timelines and will include 28 days safety and immunogenicity data after vaccination (Day 29).

Confidential Page 16 of 94

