10.4 SAMPLE SIZE AND POWER

It is planned to randomize 372 participants in the study with 186 in each of 2 cohorts who have received primary vaccination with either COVISHIELD OR COVAXIN. Assuming that the proportion of non-evaluable participants ≤ 15% (which leads to a sample size of 158 evaluable participants for each cohort), group sample sizes of 93 each in the tested vaccine group and the active control group achieve 80% power to detect non-inferiority using a one-sided, two-sample t-test. The margin of non-inferiority is -0.33. The true ratio of the means at which the power is evaluated is 1.00. The one-sided significance level (alpha) of the test is 0.025. The

CONFIDENTIAL Page 61 of 94

coefficients of variation of both groups are assumed to be 1.1. Non-inferiority of COVOVAX booster over an active control vaccine group for each cohort will be concluded separately if the lower limit of the two-sided 95% CI for the GMT ratio for both anti-S IgG antibodies and neutralizing antibodies between COVOVAX and the active control vaccine at Day 29 is > 0.67 (non-inferiority margin).

With the same sample size and randomization ratio, the study will achieve 82% power to detect non-inferiority using a one-sided, two-sample z-test for difference in two proportions of participants achieving \geq 2-fold increase. The margin of non-inferiority is -10%. The true difference of the proportion at which the power is evaluated is 0 and the proportion in the active control group is assumed 95%. The one-sided significance level (alpha) of the test is 0.025.

Sample size calculations were performed using a non-inferiority test for the ratio of two means and difference in two proportions in PASS 15.0.7 Version software.

The following table shows the evaluable sample size to demonstrate noninferiority of immune response:

	Power Evaluable sample size		ze (SS)	% Non-		
Cohort	GMR	Diff. of Prop. of participants with ≥2-fold rise	Total number of participants	COVOVAX	Control (Covishield/ Covaxin for respective cohort)	evaluable participants (Dropout rate)
COVISHIELD	80	82	158	79	79	15%
Prime cohort						
COVAXIN	80	82	158	79	79	15%
Prime cohort						

Based on sample size of each arm, the 95% confidence interval for safety events are:

True safety		(95% Exact binomial Cl	[
event rate	COVOVAX (N=93)	Active Control (N=93)	One Cohort (either COVISHIELD Prime or COVAXIN Prime) (N=186)	COVOVAX Booster Combined (N=186)	Overall (N=372)

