Estimand 1.1b, Estimand 1.2b (Co-Primary)	Difference in proportions of participants achieving ≥ 2-fold increase in anti-S IgG and nAbs 28 days after vaccination (at Day 29) between vaccines (COVOVAX booster/ Active control).	Per protocol Population	Values below the limit of quantification (LOQ) or limit of detection (LOD) will be replaced by LOQ/2 and LOD/2, respectively before log transformation.	The difference between the vaccines (COVOVAX booster - Active control) in the proportion of the participants achieving ≥ 2-fold increase in anti-S IgG nAbs 28 days after vaccination will be provided along with their two-sided 95% CIs obtained by the Miettinen and Nurminen method	Additional details for the sensitivity analysis will be included in the SAP.
	Principal stratum and Hypothetical strategy are used to understand antibody levels achieved through vaccination, without subsequent COVID-19/SARS-CoV-2 infection or use of any immune-modifying			This analysis will be performed for each type antibody (anti-S IgG or nAbs) and cohort separately. $H_0: P_T-P_C \leq -10\% \ versus$ $H_1: P_T-P_C > -10\%$	
	of any immune-modifying medications or other vaccines. While on treatment strategy is used for event death. (data until death is utilized)			Where, T =COVOVAX and C=Active Control vaccine (COVISHIELD or COVAXIN). The lower limit of the 95% CI for the for difference in proportion will be compared with a non-inferiority margin of -10% and COVOVAX vaccine will be declared non-inferior to the Control vaccine (COVISHIELD or COVAXIN) if > -10% on both anti-S IgG antibody and nAbs.	
Estimand 2 Estimand 3 (Secondary)	Proportion of participants with at least one occurrence of 1. solicited local and/ or systemic adverse event (AEs) for 7 days post-vaccination, 2. unsolicited AEs for 28 days post-vaccination and 3. SAEs throughout the study	Safety Population	None	Frequencies and estimate of the proportion of participants with at least one solicited local and systemic adverse event (AE) for 7 days post-vaccination, unsolicited AE for 28 days post-vaccination, SAE, and adverse events of special interest (AESI) throughout the study duration following vaccination will be computed by vaccine	

CONFIDENTIAL Page 75 of 94

		Main Estimation			Sensitivity
Estimand Label	Estimand Description	Analysis Set	Imputation/ Data/ Censoring Rules	Analysis Model/Method	Analysis

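### The 82% power given for the two fold-rise co-primaries is that of a simple z-test; under the planned Miettinen-Nurminen interval it is about 70% at 79 evaluable per arm

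*Protocol*

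**What the plan says.** Protocol section 10.4 plans 93 randomized per arm in each cohort. Allowing for up to 15% non-evaluable, its power table shows 79 evaluable per arm. For the fold-rise endpoints it says: "With the same sample size and randomization ratio, the study will achieve 82% power to detect non-inferiority using a one-sided, two-sample z-test". The inputs given there are a margin of -10 percentage points, a true difference of 0, one-sided alpha of 0.025, and that "the proportion in the active control group is assumed 95" percent. The table repeats 82 for both cohorts. The Protocol Summary (Statistical considerations) has the same claim: the sample size "will achieve 82% power, using a one-sided, two-sample z-test at alpha level of 0.025".

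The analysis is specified differently. Section 10.6.3, for Estimands 1.1b and 1.2b, reports the difference with "two-sided 95% CIs obtained by the Miettinen and Nurminen method" and declares non-inferiority if the lower limit exceeds -10%. The Protocol Summary agrees: the hypothesis "will be examined using the Miettinen and Nurminen method for 95% CI of the difference". Section 10.3 requires all four co-primary null hypotheses in a cohort to be rejected, two of which are fold-rise hypotheses. The protocol gives no power for the Miettinen-Nurminen method.

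**The concern.** The test that was powered is not the test that decides. Near 95% the choice matters. A simple z-test estimates its standard error from the observed proportions. The Miettinen-Nurminen score interval estimates the variance under the constraint that the true difference equals the margin. With 95% observed in both arms, that constraint moves the proportions to about 87% and 97%, where the binomial variance is larger. The lower limit is therefore further from the point estimate, and -10% is harder to exclude.

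The fold-rise hypotheses are mandatory, so an overstated power here overstates the chance of success for the whole cohort. It also changes which endpoint is the weak one. The section 10.4 table shows the GMR (80%) as slightly weaker than the fold-rise difference (82%). If the fold-rise power is nearer 70%, that order reverses, and readers of the protocol are shown a power that the specified analysis does not have.

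**Working it through.** **Inputs (section 10.4 unless stated).** Proportion in each arm 0.95 (control 95%, true difference 0); margin 0.10; one-sided alpha 0.025, so the critical value is 1.96; 93 randomized per arm; 93 × 0.85 = 79.05, so 79 evaluable per arm. Decision rule from section 10.6.3: Miettinen-Nurminen lower 95% limit above -10%.

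**Step 1: reproduce the plan's figure.**
- SE = √(2 × 0.95 × 0.05 / 79) = 0.0347
- Power = Φ(0.10/0.0347 − 1.96) = Φ(2.884 − 1.960) = Φ(0.924) = 82.2%

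This matches the stated 82%. The protocol does not say whether the variance is pooled or unpooled. With equal true rates both versions of this formula give 82.2%.

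**Step 2: large-sample power of the planned method.** The constrained proportions at a difference of -0.10 are 0.8703 and 0.9703.
- Null SE = √[(0.8703 × 0.1297 + 0.9703 × 0.0297)/79] = 0.0423
- Power = Φ[(0.10 − 1.96 × 0.0423)/0.0347] = Φ(0.490) = 68.8%
- With the Miettinen-Nurminen factor N/(N−1), N = 158, it is 68.5%

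**Step 3: exact power of the planned method.** All 80 × 80 outcome tables at 79 per arm were enumerated with binomial probabilities at 0.95 and 0.95. A table counts as a success if the score statistic against -0.10 (constrained maximum-likelihood variance with the N/(N−1) factor) exceeds 1.96. Closed-form and numerical solutions for the constrained estimates give the same power.

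| Method | Evaluable per arm | Power |
|---|---|---|
| z-test, normal formula (as stated) | 79 | 82.2% |
| z-test, exact | 79 | 80.9% |
| Miettinen-Nurminen, exact | 79 | 70.4% |
| Miettinen-Nurminen, exact | 93 (no loss) | 78.6% |

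**Step 4: error rate at the margin.** Exact one-sided error at 79 per arm with true rates of 85% and 95% is 3.4% for the z-test and 2.1% for Miettinen-Nurminen. Part of the z-test's extra power is bought by exceeding the nominal 2.5%.

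**Step 5: sensitivity to the assumed rates.** Miettinen-Nurminen exact power at 79 per arm:
- equal rates of 93%: 60.6%; 96%: 76.3%; 97%: 83.4%
- COVOVAX 96% against control 95%: 82.2%; 97% against 95%: 91.5%

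**Step 6: what the stated power would need.** Exact power is 81.4% at 95 evaluable per arm and 83.5% at 99. With 15% loss, 95/0.85 = 111.8, so 112 randomized per arm, and 99/0.85 = 116.5, so 117, against 93 planned.

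**Step 7: both fold-rise tests together.** The protocol gives no correlation between the two assays' responses, so only a range can be stated. The chance of passing both lies between 2 × 0.704 − 1 = 41% and 70%. Independence would give 0.704² = 50%. From the stated 82% the corresponding figures are 64%, 82% and 67%.

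**The case against.** The strongest reply is that the protocol makes no arithmetic slip: it names a z-test, and 82% is correct for a z-test. That is true, and the fault is better described as a mismatch between the planning test and the analysis test. It does not rescue the figure, because the power that matters to a reader is that of the rule that decides.

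Second, the 12-point gap compares an exact figure with a normal approximation. Exact against exact it is 80.9% versus 70.4%, or 10.5 points. Formula against formula it is 82.2% versus 68.5% to 68.8%, or 13 to 14 points. This is a fair refinement. The gap is large either way, and 12 points is the distance from the printed number.

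Third, 79 per arm is the worst case of a loss of at most 15%, and the result is sensitive to the assumed rates. Both are true: power is 73.3% at 84 per arm and 76.2% at 88, and it exceeds 80% if COVOVAX is slightly better or if both rates are 97%. But 82% is printed for 79 per arm at 95% with no difference. Under those rates the planned method does not reach it even with no loss.

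Fourth, the mismatch cannot produce a false non-inferiority claim. This also stands. The estimand, the decision rule and the error control are unaffected; what is misstated is the risk of an inconclusive cohort.

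**Conclusion.** The concern holds. Under the protocol's own assumptions, each fold-rise co-primary has about 70% power at 79 evaluable per arm with the planned Miettinen-Nurminen interval, not 82%, and 78.6% if nobody is lost. The chance of failing each one when the vaccines are identical is about 30% rather than 18%. The fold-rise tests, not the GMR, are then the weakest of the four mandatory hypotheses, and overall power for a cohort cannot exceed about 70% at the planned evaluable size.

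This rests on the protocol's 95% response in both arms, a true difference of 0, 15% loss and one-sided 0.025. The 70% is per endpoint. It would be higher if COVOVAX were truly better and lower if the response in both arms were below 95%.

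**What to change.** In section 10.4, in its power table (both cohorts) and in the Protocol Summary, replace 82% with the power of the planned method: about 70% at 79 evaluable per arm and about 79% at 93. Name the Miettinen-Nurminen interval as the method for which power is given. Keep that interval as the analysis; switching to the z-test to recover 82% would mean accepting a one-sided error of about 3.4%.

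The cost is wording and one figure in the table, with a less favourable number on record. No extra participants are needed to correct the statement. The sponsor should then say whether it accepts about 70% on two mandatory endpoints. Reaching at least 80% on each would take about 95 evaluable, or 112 randomized, per arm, which is a separate decision.

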10.5 ANALYSIS POPULATIONS

10.5.1 Enrolled Population

All participants who provide written informed consent, regardless of the participants screening, randomization and treatment status in the study.

Version: 4.0 Dated 21 Apr 2022

10.5.2 Randomized Population

All participants in the enrolled population who are randomized (i.e. assigned treatment).

10.5.3 Full Analysis Population

All participants in the Enrolled population who received the study vaccine and provided an evaluable serum sample post vaccination for at least one assessment. Participants in the Full Analysis population will be analyzed 'as randomized', i.e., according to the vaccine a participant was designated to receive, which may be different from the vaccine the participants actually received.

10.5.4 Safety Population

All participants who receive the study vaccine [COVOVAX or Control Vaccine (COVISHIELD or COVAXIN)]. All safety analyses will be performed using this population. Participants in the safety population will be analyzed as 'treated' (i.e. actual vaccine received).

10.5.5 Per Protocol Population

Per Protocol population will be a subset of Full Analysis population. Per Protocol population consist of all participants who received the study vaccine and provided an evaluable serum sample post vaccination for at least one assessment and have baseline (Day 1) data available, excluding any data from time points following a SARS-CoV-2 infection or major protocol deviation (defined as use of an immunosuppressant, immune-modulating medication or vaccines which interfere with assessing immunogenicity), which means subject exclusion when any of these event(s) occurs before Day 29. All immunogenicity analyses will be performed using this population. Participants in the Per Protocol population will be analyzed 'as randomized' (i.e. planned vaccine group). The review and determination for exclusion from the Per Protocol Population will be carried out in a blinded fashion by a study clinician prior to unblinding.

CONFIDENTIAL Page 63 of 94

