7.4 PARTICIPANT DISCONTINUATION

Participant discontinuation from study procedures prior to completion of the last study visit may occur for any of the following reasons:

• Dropout (defined as discontinuation initiated by a participant): Participation in the study is strictly voluntary. Participants have the right to withdraw their consent from study participation at any time and for any reason, without penalty. The participant may also initiate discontinuation due to an adverse event.

CONFIDENTIAL Page 49 of 94

- Investigator-initiated: The study investigator may, at their discretion, discontinue a
 participant from the study if they consider it to be in the participant's best interest to do
 so (e.g., for safety concerns), or if the participant does not comply with the study
 requirements.
- Lost to follow-up: For participants who fail to attend scheduled visits, study staff are to
 make at least three attempts to contact the participant prior to considering the
 participant as lost to follow-up. These attempts should be recorded in the source
 documents.
- Sponsor-initiated: For example, if the sponsor is obliged to end the study for administrative or any other reasons.
- Ineligibility (either arising during the study or retrospectively, having been overlooked at screening).

Participants who discontinue prior to administration of the vaccine will be replaced, whereas those withdrawn after administration of the vaccine will not be replaced.

The reason for and date of participant discontinuation will be documented in the source documents and relevant electronic Case Report Form (eCRF). Before entering any category as the reason for the participant's discontinuation from the study, the investigator should make every effort to investigate whether an AE may have been related to the participant's discontinuation from the study. If an AE has been associated with the discontinuation, this must be described on the discontinuation eCRF page, even if it is not the primary reason for the participant's withdrawal. For participants considered lost to follow-up, the discontinuation date for the participant to be captured on the discontinuation eCRF page is the date of the participant's last completed study visit.

In the event of participant discontinuation from the study, reasonable efforts should be made to conduct the following procedures (unless participant consent to do so has been withdrawn):

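### The Per Protocol exclusions omit receipt of the wrong study vaccine, so such participants are analysed under a vaccine they did not get

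*Protocol*

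**What the plan says.** Protocol Section 10.5.5 makes the Per Protocol population the set for all immunogenicity analyses. It requires the study vaccine, at least one evaluable post-vaccination serum sample and baseline data. Beyond that, it removes data only after a SARS-CoV-2 infection or a major protocol deviation. That term is "defined as use of an immunosuppressant, immune-modulating medication or vaccines which interfere with assessing immunogenicity". On grouping it says: "Participants in the Per Protocol population will be analyzed 'as randomized' (i.e. planned vaccine group". Exclusions are decided by a study clinician who is blinded.

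Four other sections bear on this:

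- Section 10.5.3 (Full Analysis Population) also groups by the designated vaccine, and adds "which may be different from the vaccine the participants actually received".
- Section 10.5.4 groups the Safety population by the vaccine actually received.
- Section 6.1 uses the term study vaccine for the vaccines that the sponsor provides for evaluation. A participant given the other arm's vaccine has therefore still received the study vaccine.
- Section 10.6.3 gives one supplementary analysis for the co-primary GMRs, a repeat on the Full Analysis population. For the responder differences it leaves sensitivity analyses to the SAP.

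**The concern.** A Per Protocol analysis normally sits beside an as-randomised analysis because it reflects the treatment taken as planned. Here the two sets treat a wrong-vaccine recipient identically: both keep the participant, under the vaccine not received. The protocol foresees that such cases can occur and uses the actual vaccine for safety, but does not carry the distinction into the primary immunogenicity set.

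This matters because the co-primary comparisons test non-inferiority. Mixing the arms shrinks any true difference. If COVOVAX sits at or below the margin, the shrinkage moves the estimate toward passing, and no comparative immunogenicity analysis fixed in the protocol would show the result without these participants.

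**Working it through.** **Inputs, Section 10.4 unless noted.**

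- Alpha: "The one-sided significance level (alpha) of the test is 0.025".
- True ratio for power: "The true ratio of the means at which the power is evaluated is 1.00".
- Variability: the "coefficients of variation of both groups are assumed to be 1.1".
- Margins: 0.67 for the GMR and -10 percentage points for the responder difference (also Section 10.6.5). The control responder proportion is 95%.
- Size: 93 randomised per arm and 15% non-evaluable, so 93 × 0.85 = 79.05, or 79 evaluable per arm as in the Section 10.4 table.
- Number of wrong-vaccine recipients: not given. Assumed range 1 to 8 of 79 per arm.

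**Step 1: reproduce the plan's power.** The log-scale SD is sqrt(ln(1 + 1.1²)) = 0.8905. The distance to the margin is -ln(0.67) = 0.4005. With 79 per arm, SE = 0.8905 × sqrt(2/79) = 0.1417 and the non-centrality is 0.4005/0.1417 = 2.83. The non-central t with 156 df gives 80.2%. The text says that "group sample sizes of 93 each in the tested vaccine group and the active control group achieve 80% power to detect non-inferiority". The 80% belongs to the 79 evaluable per arm; 93 evaluable would give 86.2%. For responders, SE = sqrt(2 × 0.95 × 0.05/79) = 0.0347 and Φ(0.10/0.0347 - 1.96) = 82.2%, against the stated 82%. Both figures reproduce.

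**Step 2: dilution.** Suppose k of 79 in each arm receive the other arm's vaccine and are analysed as randomised. The expected difference is multiplied by (1 - 2k/79):

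- expected GMR = exp[(1 - 2k/79) × ln(true GMR)]
- expected responder difference = (1 - 2k/79) × true difference

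A true GMR of 0.60 is then expected to appear as 0.616 with k = 2 and 0.632 with k = 4.

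**Step 3: error at the margin.** Set the true GMR to 0.67. With m = k/79, the within-arm variance becomes 0.8905² + m(1 - m) × 0.4005². The chance of declaring non-inferiority comes from the non-central t. For k = 4:

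- the expected log GMR is 0.8987 × (-0.4005) = -0.3599
- the excess over the margin is 0.4005 - 0.3599 = 0.0406
- the SE is 0.1424, so the non-centrality is 0.285, which gives 4.7%

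For responders, the true proportions are 85% and 95% and a normal approximation is used.

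| Swaps per arm | Expected GMR | Error, GMR test | Expected responder difference | Error, responder test |
|---|---|---|---|---|
| 0 | 0.670 | 2.5% | -10.0 points | 2.5% |
| 1 | 0.677 | 2.95% | -9.75 | 2.8% |
| 2 | 0.684 | 3.5% | -9.5 | 3.2% |
| 4 | 0.698 | 4.7% | -9.0 | 4.1% |
| 8 | 0.727 | 8.1% | -8.0 | 6.3% |

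**Step 4: other true values.** At a true GMR of 1 the log ratio is zero, so swaps leave the estimate at 1 and power at 80.2%. At a true GMR of 1.5, four swaps per arm lower the expected GMR to 1.44, and the chance of declaring non-inferiority moves from 99.99% to 99.96%.

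**Step 5: cost of excluding them.** At a true GMR of 1, removing k per arm from the 79 lowers power from 80.2% to 79.7% (k = 1), 79.2% (k = 2) or 78.1% (k = 4).

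**The case against.** The strongest reply is that such errors should be very rare. This is a single-dose trial with IWRS allocation, designated unblinded staff to prepare and give the vaccine, and an unblinded CRO monitor (Section 7.2). Four swaps in each arm would mean about 5% of participants received the wrong vaccine. Success in a cohort also requires all four co-primary tests to pass (Section 10.3), so the overall error cannot exceed the single-test figure. All of this stands, and it keeps the expected effect small.

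It might also be said that the other arm's vaccine is an interfering vaccine and so already excluded. The wording does not bear this well. The estimand descriptions refer to other vaccines, meaning those outside the assigned study vaccination, and an as-randomised rule would have no work to do if wrong-vaccine recipients were already out.

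The SAP is not shown and may add exclusions. The point does not rest on its silence: the protocol itself fixes a closed definition and a grouping rule.

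A reader might go further and infer that participants found ineligible after vaccination, or sampled outside the Day 29 window, bias the result in the same way. The documents do not support this:

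- Section 10.5.5 sets no earliest date for the infection or interfering vaccine, so it may already exclude prior COVID-19 or a prior booster.
- The GMR model in Section 10.6.3 adjusts for the interval from dose 2 to booster.
- Section 7.4 lists "Ineligibility (either arising during the study or retrospectively, having been overlooked at screening" as a reason for discontinuation, so some of these participants may give no Day 29 sample.
- Dilution by those who remain would need an assumption about how they respond to each vaccine.
- Sample windows are routine SAP detail, and no bias from them is shown.

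**Conclusion.** The point holds in a narrow form. As written, a wrong-vaccine recipient stays in the primary set under the vaccine not received, and the supplementary Full Analysis repeat does the same. Where COVOVAX is truly inferior, this favours a false non-inferiority claim: single-test error at a GMR of 0.67 rises from 2.5% to 2.95% with one swap per arm and 4.7% with four.

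It would be wrong to infer that the bias always favours non-inferiority. It vanishes at a GMR of 1, the value at which the plan is powered, and slightly disadvantages COVOVAX above 1.

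The figures rest on assumed counts, equal numbers of swaps in the two arms, swaps only between the two vaccines of a cohort, and an unadjusted comparison at the planned SD rather than the planned ANCOVA. With few errors the effect is modest, but it bears on the primary set and costs little to remove.

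**What to change.** Add to Section 10.5.5 that participants whose vaccine received differs from the vaccine randomised are excluded from the Per Protocol population. Once they are out, grouping by randomised or by received vaccine gives the same result, so the as-randomised sentence can stay.

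The blinded clinician cannot see these cases. The exclusion should therefore be applied by fixed rule, without judgement, by the unblinded CRO statistician already provided for in Section 7.2, before sponsor personnel see group-wise data at the Day 29 interim analysis. The Full Analysis repeat remains as the as-randomised analysis.

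The cost is one sentence and possibly a few participants. If they fall within the 15% non-evaluable allowance, the planned power stands. If they come on top of it, the loss is about 0.5 points of GMR power per swap per arm.
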